5.1 Sample Size Considerations

Approximately 360 subjects are to be randomized into 1 of 4 treatment groups in a 1:1:1:1 ratio, resulting in around 90 subjects per group.

With a sample size of 90 subjects per arm, there will be at least 84% power to detect a treatment difference of 20% in SRI(4) response rates between the BID BMS-986165 treatment arms and placebo.

5.2 Randomization

Approximately 360 subjects are planned to be randomized via IRT in a 1:1:1:1 ratio to 1 of 4 treatments: BMS-986165 3 mg BID, 6 mg BID, and 12 mg QD, or placebo. Randomization is stratified by screening CS dose (≥ 10 mg/day or < 10 mg/day), screening SLE Disease Activity Index 2000 (SLEDAI-2K) score (≥ 10 or < 10), and region (North America, Latin America, Japan [other randomization factors will not be applied in Japan], and rest of world).

5.3 Unblinding Information

Investigative site staff, Sponsor and designated personnel, and subjects and their families will remain blinded to treatment assignments. After the week 48 database lock, the Sponsor and designated personnel will be unblinded. Those subjects who are enrolled or will enroll in study IM011-074 will continue to remain blinded to their treatment assignment (including investigative site staff and subjects' families) in this study after the week 48 database lock. Those subjects who do not enroll or will not enroll in study IM011-074 may be unblinded to their treatment assignment (including investigative site

Sponsor: Bristol-Myers Squibb
Protocol no: IM011021

staff) after the week 48 database lock. However, if there is a medical emergency or pregnancy where knowledge of investigational product (IP) is critical to the subject's management the blind may be broken by the Investigator.

The Data Monitoring Committee (DMC) provides oversight of safety consideration throughout the study. A separate unblinded team, comprised of an unblinded Independent Reporting Statistician (IRS) and unblinded programmer(s), will produce output for the DMC using masked treatments. Treatment decodes may only be requested by DMC Chair and will be provided by the IRS. Data summaries and listings will be transmitted via a secure portal by IRS to only the DMC members. Additional details regarding the DMC process and unblinding are provided in the DMC charter.

Designated staff of BMS may be unblinded prior to database lock to facilitate the bioanalytical analysis of PK and biomarker samples and immunogenicity.

5.4 Summary of Changes to Version 2.0 of SAP

No analyses were performed prior to the revision of this SAP.

5.4.1 Changes due to protocol amendments after finalization of SAP V1.0

2. Revised the testing strategy to be used for the primary and secondary endpoints (Section 9.3.1.4 of protocol)
3. Week 48 endpoints moved into the multiplicity-controlled hierarchy for better alignment with regulatory guidance documents
4. Non-responder imputation (NRI) section updated: updated to clarify that this NRI is applicable to the primary and secondary endpoints at Week 32 and Week 48.
5. Single randomization stratum combining Region (North America, Latin America, Rest of World, Japan [other stratification factors will not be applied in Japan]), CS dose at baseline (≥ 10 mg/day or < 10 mg/day) and SLEDAI-2K at baseline (≥ 10 or < 10) added for logistic regression, Cochran-Mantel-Haenszel and repeated measures analysis: Clarification of how to handle the lack of CS and SLEDAI-2K stratification within Japanese subjects
6. Revised the testing hierarchy for the QD and BID branches: Testing strategy revised to align with revision of the Week 48 endpoints to secondary endpoints. The revised testing strategy ensures the familywise Type I error is protected for the primary and secondary endpoints.
7. The planned 32-week database lock has been removed: Since the key secondary endpoints will now be assessed at Week 48 no database lock will occur until all randomized subjects have completed 48 weeks of double-blind treatment (or have discontinued)

5.4.2 Additional Changes to SAP V2.0

1. Changes to the description of the composite endpoints for efficacy (aligned with source literature):
 - a. SRI response:
 - i. correction: no new BILAG A (severe disease activity) and (instead of "or" as indicated in the protocol) not more than 1 new BILAG B (moderate disease activity) organ domain grade since baseline
 - ii. clarification: "new BILAG grade" should be interpreted as "worsened BILAG grade compared to baseline"

Sponsor: Bristol-Myers Squibb
Protocol no: IM011021

- iii. correction: response only if PGA change from baseline <0.3 (instead of " ≤ 0.3 " as implied in the protocol description) (see Furie et al. Arthritis Rheum. 2009 61(9): 1143–1151; and [Furie R, Petri MA, Strand V, et al. Clinical, laboratory and health-related quality of life correlates of Systemic Lupus Erythematosus Responder Index response: a post hoc analysis of the phase 3 belimumab trials. Lupus Science & Medicine 2014;1: e000031. doi:10.1136/lupus2014-000031](#))
 - b. BICLA response: "new BILAG grade" should interpreted as "worsened BILAG grade compared to baseline"
 - c. LLDAS response: "new BILAG grade" should interpreted as "worsened BILAG grade compared to previous assessment"
 2. Added for clarification to the CTP: All hypothesis test will be based on Wald tests for odds ratio estimates for comparisons of the treatment groups and the placebo group obtained from the logistic regression models
4. Removal of per protocol analyses
5. Removal of all LOCF analyses
6. Modified sensitivity analyses, including addition of a treatment policy approach
7. Added a tipping point analysis for the primary endpoint
9. Various changes to format and structure to improve clarity
11. Refinement of NRI imputation method including the list of prohibited medications
12. Updated PK and Biomarker analyses

5.5 Summary of Changes to Version 3.0 of SAP

No analyses were performed prior to the revision of this SAP.

1. Added clarification for the first dose date in section 7.1
2. Added one additional condition in sections 11.7.1 and 11.7.2.2:
 - a. Subjects takes any medications included in protocol Appendix 7 between first dose date and efficacy assessment visit
3. Deleted one condition in sections 11.7.1 and 11.7.2.2:
 - a. Initiations and/or increases which occur for less than 4 days are permitted
4. Deleted the bar chart in sections 11.7.1, 11.7.2.3 and 11.7.2.4
5. In section 11.7.1, in case the logistic regression model fit is not stable the region stratification factor may be removed from the model. The stratification factors were updated to: CS dose ≥ 10 mg/day Yes or No, SLEDAI-2K score ≥ 10 Yes or No, and Japan.
6. Added clarification for analysis time points in section 11.7.2.5
7. Changed "interferon regulated genes" to "interferon" in section 11.7.4
8. Added "at baseline" for subgroup analyses referring to CS Use, anti-malarial use, and immunosuppressant use in section 11.7.4
10. Added clarification for analysis time points in section 11.7.5
11. Deleted the following condition in section 11.8.4:

Sponsor: Bristol-Myers Squibb
Protocol no: IM011021

- a. No other immediately apparent possible causes of liver function test elevation and hyperbilirubinemia, including, but not limited to, viral hepatitis, preexisting chronic or acute liver disease, or the administration of other drug(s) known to be hepatotoxic.
12. Modified the QTcF calculation in section 11.8.6
13. Updated the pharmacokinetic analyses in section 12.0
14. Updated the biomarker analyses in section 13.0
15. Updated the biomarker listing in [appendix 6](#)

5.6 Summary of Changes to Version 4.0 of SAP

No analyses were performed prior to the revision of this SAP.

1. Deleted "between visits as collected from 'Rescue Medication' eCRF page" in section 11.5.2

6.0 Study Variables

6.1 Efficacy Assessments

The following efficacy procedures or tools will be used to assess subjects' SLE disease activity during the study:

British Isles Lupus Assessment Group (BILAG)-2004

The BILAG-2004 grades are based on recording disease activity for 97 items in 9 different organ systems (constitutional, mucocutaneous, neuropsychiatric, musculoskeletal, cardiorespiratory, gastrointestinal, ophthalmic, renal, and hematological, see Appendix 10 of the study protocol). Each item is measured qualitatively by clinical observation (yes/no, not present/improving/same/worse/new) based on lupus activity over the past 4 weeks compared with the previous 4 weeks or quantitatively by measuring hematologic and renal lab values. For abnormal lab values, the item is noted as SLE related or not SLE related. Based on scores of the 97 items, an alphabetical grade is derived for each organ system representing 5 levels of disease with A being the highest level of disease activity. The grades are given a numerical score equivalent:

- A (very active) = 12
- B (moderate disease activity) = 8
- C (mild stable disease) = 1
- D (no current disease activity but the system had previously been affected) = 0
- E (no current or previous disease activity) = 0

A global BILAG-2004 score (range from 0 to 108) is derived by summing-up the numerical score equivalents for each organ system. Grades are assigned by central reviewers based on BILAG-2004 Index Scoring along with grading conventions. The detailed grading conventions are documented in the Central Review Plan including the handling of missing data when assigning the grades. Grades assigned in 'BILAG Grading' eCRF page will be used for analysis purpose.

SLEDAI-2K

The SLEDAI-2K is a global index based on weighted scores for each of 24 clinical findings rated as present or absent at the time of the visit or in the last 30 days (see Appendix 11 of the Study Protocol). The total score for SLEDAI-2K ranges from 0 to 105 with higher scores representing higher disease activity. The total score collected in 'SLEDAI-2K' eCRF page will be used for analyses. The detailed grading conventions are documented in the Central Review Plan including the handling of missing data when assigning the grades.

Cutaneous Lupus Erythematosus Disease Area and Severity Index (CLASI)

Sponsor: Bristol-Myers Squibb
Protocol no: IM011021

CLASI assesses cutaneous disease activity and damage by body surface area (see Appendix 12 of the study protocol). Only the CLASI activity score derived in 'Cutaneous LE Disease Area and Severity Index (CLASI)' eCRF page will be used in this study.

For disease activity, points are given for presence of erythema, scale, hypertrophy, mucous membrane lesions, recent hair loss, and physician-observed alopecia and a total activity score is derived. The CLASI total activity score (CLASI-A) ranges from 0-70, where a higher score is associated with high disease activity.

For the damage assessments, points are given for dyspigmentation, scarring, and scarring alopecia. A total damage score is derived. The CLASI total damage score (CLASI-D) ranges from 0 – 56, where a higher score is associated with larger extent of damage.

40-joint Count

Each of 40 joints is evaluated for the presence/absence of tenderness, swelling, and simultaneous presence/absence of both tenderness and swelling. The following joints will be evaluated: the bilateral wrists, elbows, ankles, knees, interphalangeal joints of the thumb, individual proximal interphalangeal joints of the hand, second through fifth metacarpophalangeal joints of the hand, and individual metatarsophalangeal joints of the feet (which make up the 36-joint count). Bilateral first metacarpophalangeal joints and shoulders are also included, bringing the joint count to 40. From the above assessment, joint counts will be calculated for:

- Tender joints (0-40)
- Swollen joints (0-40)
- Tender and swollen joints (0-40): joints that are both tender and swollen (= active) are counted.

A larger joint count indicates more severe disease. The total joint counts collected from the eCRF will be used for analysis.

Physician's Global Assessment (PGA) of Disease Activity

The Physician's Global Assessment of Disease Activity (PGA) will be assessed using a 3-point visual analog scale (VAS) as the subject's average disease activity over the past 30 days. A score of 0 represents no disease activity and a score of 3 represents severe disease activity. An approximate score at tenth intervals between 0 and 3 (inclusive) will be reported.

Sponsor: Bristol-Myers Squibb
Protocol no: IM011021

6.2 Composite Measures

The following composite measures will be determined based on assessments described above.

BILAG-based Composite Lupus Assessment (BICLA)

BICLA response is achieved if all of the following criteria are met:

- Improvement in all organ systems with activity graded as BILAG-2004 A or B at baseline
- No new organ system with activity graded as BILAG-2004 A and no more than 1 new organ system with activity graded as BILAG-2004 B since baseline
- No increase from baseline in SLEDAI-2K (change from baseline of ≤ 0 score)
- No increase from baseline $\geq 10\%$ (or ≥ 0.3 points) in the Physician's Global Assessment of Disease Activity on a 3-point VAS
- No discontinuation of IP or use of restricted medications beyond the protocol allowed threshold before assessment (refer to [section 11.7.2](#) with more details)

SLE Responder Index (SRI[X])

The SRI is a composite responder endpoint. SRI(X) response is achieved if all of the following criteria are met:

- Reduction from baseline of $\geq X$ points in the SLEDAI-2K
- No new BILAG A (severe disease activity) and not more than 1 new BILAG B (moderate disease activity) organ domain grade since baseline
- No worsening from baseline in the Physician's Global Assessment of Disease Activity scale by > 0.3 points

[figure not shown]
[figure not shown]
Lupus Low Disease Activity State (LLDAS)

LLDAS response is achieved if all of the following criteria are met:

- SLEDAI-2K ≤ 4 , with no activity in major organ systems (renal, central nervous system, cardiopulmonary, vasculitis, fever) and no hemolytic anemia or gastrointestinal activity (measured as maintaining a D or E score in the BILAG gastrointestinal body system)
- No new lupus disease activity compared with the previous assessment measured as no new or worsening individual BILAG parameters
- Physician's Global Assessment of Disease Activity ≤ 1
- Prednisone or equivalent dose ≤ 7.5 mg/day
- Well tolerated standard maintenance doses of immunosuppressive drugs and approved biologic agents (refer to [section 11.7.2](#) with more details)

[figure not shown]
Sponsor: Bristol-Myers Squibb

Protocol no: IM011021

Sponsor: Bristol-Myers Squibb

Protocol no: IM011021

Sponsor: Bristol-Myers Squibb
Protocol no: IM011021

6.4 Safety

Safety data to be collected includes physical examination and measurements, vital signs, 12-lead ECG, hematology, clinical chemistry, urinalysis, coagulation, fasting lipid and glucose, pregnancy test results, concomitant medication use, and incidence and severity of all reported AE and SAEs. The planned time points for all safety assessments are listed in the [Appendix 2](#). The change from baseline at each scheduled time point during the treatment period will be calculated for relevant measures.

6.5 Predetermined Covariates and Prognostic Factors

The following stratification factors are applied in this study:

- CS dose (≥ 10 mg/day or < 10 mg/day)
- SLEDAI-2K score (≥ 10 or < 10)
- Region (North America, Latin America, Japan, rest of world)

However, as CS dose and SLEDAI-2K score are not applied in Japan, the levels for the factor that is used in the analysis to represent the randomization strata is redefined as follows:

1. CS dose = ' ≥ 10 mg/day', SLEDAI-2K score = ' ≥ 10 ', Region= 'North America' ;
2. CS dose = ' ≥ 10 mg/day', SLEDAI-2K score = ' ≥ 10 ', Region= 'Latin America' ;
3. CS dose = ' ≥ 10 mg/day', SLEDAI-2K score = ' ≥ 10 ', Region= 'rest of world' ;
4. CS dose = ' ≥ 10 mg/day', SLEDAI-2K score = ' < 10 ', Region= 'North America' ;
5. CS dose = ' ≥ 10 mg/day', SLEDAI-2K score = ' < 10 ', Region= 'Latin America' ;
6. CS dose = ' ≥ 10 mg/day', SLEDAI-2K score = ' < 10 ', Region= 'rest of world' ;
7. CS dose = ' < 10 mg/day', SLEDAI-2K score = ' ≥ 10 ', Region= 'North America' ;
8. CS dose = ' < 10 mg/day', SLEDAI-2K score = ' ≥ 10 ', Region= 'Latin America' ;
9. CS dose = ' < 10 mg/day', SLEDAI-2K score = ' ≥ 10 ', Region= 'rest of world' ;
10. CS dose = ' < 10 mg/day', SLEDAI-2K score = ' < 10 ', Region='North America';
11. CS dose = ' < 10 mg/day', SLEDAI-2K score = ' < 10 ', Region='Latin America';
12. CS dose = ' < 10 mg/day', SLEDAI-2K score = ' < 10 ', Region='rest of world';
13. CS dose = Not Applicable, SLEDAI-2K score = Not Applicable, Region='Japan';

The above redefined stratification factor collected from IVRS system will be included in statistical analysis models or be used to examine treatment effect. For subgroup analysis, the value of the above redefined stratification factor collected on the eCRF will be used.

6.6 Pharmacokinetic and Pharmacodynamic Variables

The pharmacokinetics of BMS-986165 and its metabolite BMT-153261 will be derived from plasma concentration versus time data. Biomarker data will be collected through serum, plasma, and urine samples to gain further understanding of the PD effects of BMS-986195. These samples will be analyzed for markers of tissue damage and regeneration including serum complement, anti-dsDNA and other autoantibodies, blood RNA for interferon-regulated gene (IRG) and steroid signature, genome-wide expression, and inflammatory markers.

Blood samples for pharmacokinetics and interferon-regulated gene (IRG) assessment will be collected predose and postdose at pre-specified study days and times. Actual sample times will be recorded and missed samples will be noted.

Sponsor: Bristol-Myers Squibb
Protocol no: IM011021

For a substudy of approximately 120 subjects, samples will be collected anytime on Days 2 and 3 for blood RNA and inflammatory markers.

Blood flow cytometry data will also be collected in a substudy defined by geography and accessibility to the analyzing lab. Study will occur in USA and Europe.

7.0 Definitions

7.1 General

The following data handling conventions will be used for general analysis:

Term	Definition
Study Day	The assessment date – date of first dose + 1. When the assessment date is before the date of first dose then study day is calculated as the assessment date - date of first dose.
Baseline	Baseline is defined as the last non-missing measurement prior to dosing on Day 1 (Week 0). If the measurement on Day 1 is missing or not available, then the last available measurement during the screening period will be used as a baseline.
Baseline CS Dose Categorized	For subjects taking CS at screening, the dose (prednisone or equivalent) must be stable for at least 2 weeks before the screening visit and must remain stable until randomization. The last CS dose during the screening period will be considered the baseline dose. For subjects not taking CS at screening, the baseline dose will be 0. Baseline CS Dose will be categorized as ≥ 10 mg/day or < 10 mg/day prednisone or equivalent for stratification. Baseline CS dose categorization will be from baseline CS dose eCRF form.
Change from Baseline	Change from baseline is defined as (value at post-baseline visit – value at baseline).
Concomitant and Prior Medication	Prior medications are defined as medications with a start or stop date prior to the first dose of study treatment. Concomitant medications are defined as any medication that occurred (continued, started, or stopped) on or after first dose of study medication and on or before last dose of study medication.
End of Study (EOS) Date	The EOS date is the date recorded on the eCRF that a randomized subject either discontinued or completed the study. If the subject is lost to follow-up, the EOS date will be the date of the last visit assessment obtained.
First Dose Date	The date a subject received their first dose on Day 1 as recorded in the 'Exposure - PK Sampling' eCRF form, given that the first dose should be entered even if no PK sampling is collected at Day 1. Or if the first dose date is not collected in the 'Exposure - PK Sampling' eCRF form, the earliest drug dispensation date should be used.
Last Dose Date	The Date of Last Dose of Study Treatment on 'End of Treatment' eCRF form for a randomized subject.
Percent Change from Baseline	Percent change from baseline is defined as $([\text{value at post-baseline visit} - \text{value at baseline}] / \text{value at baseline}) \times 100$. If the baseline value is 0 and the post-baseline value is also 0, then the percent change from baseline is set to 0.

Sponsor: Bristol-Myers Squibb
Protocol no: IM011021

7.2 Analysis Visits Windows

Subjects do not always adhere strictly to the visit schedule timing in the protocol. Therefore, the designation of visits during the study period will be based on the day of evaluation relative to the Day 1 of the trial (day of first dosing = study Day 1) rather than the nominal visit recorded in the case report form (CRF). Visit window based on the study day (regardless the visit labeling) will be applied for efficacy analysis and safety analysis. Each efficacy and safety measurement will be windowed. In case that two or more measurements exist in a certain visit window, the one closest to the target day will be selected. If still more than one measurements are selected, the later one will be selected for analysis.

Efficacy measurements up to last dose will be used for windowing.

Analysis Visit	Target Day	Study Day Range
Baseline	1	[-28, 1]
Week 2	15	[2, 22]
Week 4	29	[23, 43]
Week 8	57	[44, 71]
Week 12	85	[72, 99]
Week 16	113	[100, 127]
Week 20	141	[128, 155]
Week 24	169	[156, 183]
Week 28	197	[184, 211]
Week 32	225	[212, 239]
Week 36	253	[240, 267]
Week 40	281	[268, 295]
Week 44	309	[296, 323]
Week 48	337	[324, 351]
Safety Follow-up	EOT + 30	

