8.3.8 Potential Drug-Induced Liver Injury

Wherever possible, timely confirmation of initial liver-related laboratory abnormalities should occur prior to the reporting of a potential DILI event. All occurrences of potential DILIs, meeting the defined criteria, must be reported as SAEs (see [APPENDIX 3](#) for reporting details).

Potential DILI is defined by presence of all of the following characteristics:

- ALT or AST elevation $> 3 \times$ ULN
- total bilirubin $> 2 \times$ ULN, without initial findings of cholestasis (elevated serum alkaline phosphatase)
- no other immediately apparent possible causes of AST or ALT elevation and hyperbilirubinemia, including, but not limited to, viral hepatitis, preexisting chronic or acute liver disease, or the administration of other drug(s) known to be hepatotoxic

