11.0 Statistical Methods

Unless otherwise noted, variables will be reported using summary statistics according to the below methods by treatment group and analysis visit defined in [section 7.2](#).

Categorical variables will be summarized using frequency distributions (counts and percentages). Percentages will be rounded to one decimal place, and percentages will not be displayed for zero counts.

For continuous variables summary statistics will include the number of observations (n), mean, standard deviation (SD), median, minimum, maximum, 25th percentile (Q1), and 75th percentile (Q3). The median, minimum, maximum, Q1, and Q3 values will be displayed to the same level of precision as the raw data, the mean to a further decimal place and the SD to two additional decimal places.

P-values will be displayed to 3 decimal places, with values less than 0.001 presented as <0.001.

All data will be listed by subject, analysis visit and treatment group.

All statistical analysis and reporting will be done using SAS® Version 9.4 or higher (SAS Institute, Inc.).

Sponsor: Bristol-Myers Squibb
Protocol no: IM011021

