11.8.4 Laboratory Data

Laboratory parameters will be summarized using both the International System (SI) of Units and conventional system of Units, unless otherwise specified. Summaries will be provided separately by different panels including hematology, general chemistry, chemistry - hepatobiliary, chemistry - renal function tests, chemistry - coagulation, and urinalysis. Only lab assessments with collection date up to last dose day +30 days post last dose day or up to first dose day of study IM011-074 for roll over subjects will be summarized. Data will be summarized by analysis visit, as applicable. The following summaries will be provided for each parameter:

- Absolute and change from baseline values
- Laboratory abnormalities (as determined by Controlled Terminology Criteria for Adverse Events [CTCAE v5.0] grading) presented as the worst postbaseline toxicity group

Sponsor: Bristol-Myers Squibb
Protocol no: IM011021

- Shifts from baseline to maximum postbaseline value
 - Potential drug induced liver injury (DILI) is defined as a subject who meets the following criteria on the same assessment date:
 - 1) ALT or AST elevation >3 times ULN
AND
 - 2) Total bilirubin >2 times ULN
AND
 - Normal serum alkaline phosphatase (No initial findings of cholestasis)
 - ALT or AST elevation >5 times ULN
- All abnormalities in laboratory data will be provided in listings.

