11.8.6 ECG

Summary statistics will be presented for ECG observed values, change from baseline values for all ECG parameters by treatment group and analysis visit.

The summaries of marked abnormalities at any timepoint post-baseline will also be tabulated for definitions provided as below.

- Absolute and change from baseline values
- Marked abnormalities defined by the below categories:
 - QT interval corrected using Fridericia's formula (QTcF):
 - 450 -< 480 msec
 - 480 -< 500 msec

Sponsor: Bristol-Myers Squibb
Protocol no: IM011021

- ≥ 500 msec
 - $30 < \text{change from baseline} \leq 60$ msec
 - Change from baseline > 60 msec
 - Males: < 450 msec, ≥ 450 msec
 - Females: < 470 msec, ≥ 470 msec
- PR interval ≥ 200 msec
 - QRS interval ≥ 200 msec

In cases where QTcF is missing, then QTcF will be derived using the following definition: $QTcF = QT / (RR^{1/3})$, where RR (seconds) = $60 / \text{HR}$. In case where both QTcF and QT are missing, then QTcF will be derived using the following definition: $QTcF = QTcB / (RR^{1/6})$, where RR (seconds) = $60 / \text{HR}$.

Additionally, all ECG data will be provided in a listing.

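### SAP 7.2 keeps one safety value per visit window without exception, which conflicts with the worst-grade, maximum-shift, potential-DILI and any-time safety tables in 11.8.4–11.8.6

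*SAP*

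**What the plan says.** SAP 7.2 covers safety as well as efficacy: "Visit window based on the study day (regardless the visit labeling) will be applied for efficacy analysis and safety analysis". It then says "Each efficacy and safety measurement will be windowed". Where a window holds several values, "In case that two or more measurements exist in a certain visit window, the one closest to the target day will be selected", and for ties, "If still more than one measurements are selected, the later one will be selected for analysis". The only restriction written there is a last-dose cut-off for efficacy data. Severity has no priority, and unscheduled values are not mentioned.

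SAP 11.0 makes these analysis visits the default reporting unit: "variables will be reported using summary statistics according to the below methods by treatment group and analysis visit defined in" section 7.2. The default yields to anything stated elsewhere.

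The safety sections ask for extremes:

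- **11.8.4, laboratory:** abnormalities by CTCAE grade, "presented as the worst postbaseline toxicity group"; shifts from baseline to the maximum postbaseline value; potential DILI, with all criteria met on one sampling date; and ALT or AST above 5 times ULN.
- **11.8.5, vital signs:** marked abnormalities at any time after baseline.
- **11.8.6, ECG:** "The summaries of marked abnormalities at any timepoint post-baseline will also be tabulated".

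Protocol 8.3.8 foresees off-schedule testing: wherever possible, "timely confirmation of initial liver-related laboratory abnormalities should occur prior to the reporting of a potential DILI event".

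**The concern.** Taking the value nearest the target day is sensible for by-visit means, where each subject should contribute one value at a comparable time. It is the wrong input for a worst-value table. Unscheduled tests tend to be taken because something looks abnormal, and they usually share a window with a scheduled visit. A maximum taken over pre-selected values is not the postbaseline maximum.

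The rule can also work the other way. A scheduled abnormal value is removed when a later, normal retest lies nearer the target day.

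At stake are the between-arm tabulations of peak toxicity. Creatine kinase is included, because SAP 11.8.2 sends CK elevations to the laboratory summaries as CTCAE grade 2 or higher. Two programmers, one starting from 7.2 and the other from 11.8.4–11.8.6, could produce different tables and each could cite the SAP.

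**Working it through.** The plan states no figure on this point, so there is none to reproduce. The check has a textual part and an arithmetical part.

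**1. The texts side by side.** Section 7.2 selects one value per window for analysis and names no safety exception. Sections 11.8.4–11.8.6 ask for the worst, the maximum, or any occurrence. Neither says whether non-selected or unscheduled values enter those tables. Marked vital-sign abnormalities and two of the QTcF categories also use change from baseline, which SAP 7.1 defines at a postbaseline visit. That ties these tables back to the visit structure.

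**2. Inputs for the literal reading.**
- Windows (SAP 7.2): 13 postbaseline windows from Week 2 to Week 48, contiguous over Days 2–351. Two are 21 days long and eleven are 28 days, so 2×21 + 11×28 = 350 days.
- Scheduled-visit tolerance (protocol Tables 2 and 3): ±3 days.
- Assumption: the scheduled visit falls at offset s = −3, …, 3 days from target, equally likely, with a retest k days later in the same window. The documents give no retest frequency or timing.

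**3. Rule.** The retest is kept if |s + k| ≤ |s| (the later value wins a tie). Otherwise it is discarded.

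| Lag k (days) | Discarded, of 7 offsets |
|---|---|
| 2 | 4 |
| 3 | 5 |
| 4 | 5 |
| 5 | 6 |
| 6 | 6 |
| 7, 8, 9, 10 | 7 each |

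- Lags 2–10: 4 + 5 + 5 + 6 + 6 + 4×7 = 54 of 9×7 = 63, or 86%.
- Lags 3–7: 5 + 5 + 6 + 6 + 7 = 29 of 35, or 83%.
- Lags of 7 days or more: always discarded.
- In the 63 − 54 = 9 combinations where the retest is kept, the scheduled value is dropped.

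**4. Actual window edges.** The Week 2 window runs only 7 days past its target, so some long lags fall into the Week 4 window. Counting only pairs that share a window, 42 of the 63 combinations remain for Week 2, and 42 − 9 = 33 of them discard the retest. The other twelve windows contribute 12×63 = 756 pairs and 12×54 = 648 discards. The total is (648 + 33)/(756 + 42) = 681/798, or 85%.

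**5. Any other day in the window.** With a scheduled value within ±3 days of target, a second value more than 3 days off target can never be selected. Those days number 2×14 + 11×21 = 259 of 350, or 74%. If the second value falls with equal chance on any other day of the window, it is discarded in 2086 of 7×(2×20 + 11×27) = 2359 combinations, or 88%.

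**6. A hypothetical potential-DILI case.** In the Week 8 window (Days 44–71, target Day 57), suppose Day 57 shows ALT 2.5×ULN. Day 61 shows ALT 6×ULN, bilirubin 2.5×ULN and normal alkaline phosphatase. Day 61 meets all the SAP 11.8.4 criteria on one date. The distances from target are 0 and 4 days, so Day 57 is selected. The subject appears neither as potential DILI nor in the ALT/AST above 5×ULN count for that window.

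**7. ECG.** Postbaseline ECGs are scheduled only at Weeks 4, 8, 12, 32 and 48. The other 13 − 5 = 8 windows have no scheduled recording, so a lone unscheduled ECG there is kept.

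**The case against.** The strongest reply is that 11.8.4–11.8.6 are the more specific text and already ask for the worst, the maximum, or any occurrence. Potential DILI is keyed to sampling date, not analysis visit. SAP 11.0 gives way to contrary statements, and 11.8.4 uses analysis visits only where they apply. Section 11.8.4 also admits laboratory data by collection date, up to 30 days after last dose or the first dose in the extension study. The numbered windows stop at Day 351, and Safety Follow-up has a target but no day range. All this makes use of every value the likely intent.

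That stands as a reading of intent, but it does not settle the specification. The collection-date sentence limits which laboratory results are summarised without lifting the selection in 7.2. It and the where-applicable qualifier appear for laboratory data only; vital signs and ECG have just the any-time wording to set against an unqualified windowing rule.

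Three stronger inferences are not supported:

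- **A reader might infer that the SAP definitely excludes unscheduled and peak values.** No sentence says so, and the wording of the defining sections points the other way.
- **A reader might infer that raised ALT at one visit and raised bilirubin at a later retest make a potential-DILI case lost to windowing.** The same-date criterion decides that. Unless the retest date itself also shows the transaminase criterion and normal alkaline phosphatase, the subject is not a case even with every value used.
- **A reader might infer that safety signals vanish.** Protocol 8.3.8 requires potential DILI to be reported as a serious adverse event. Protocol 8.3.7 sends clinically significant laboratory results to adverse event reporting, and SAP 11.8.4 lists all laboratory abnormalities. These keep the individual records, but a listing is not a between-arm table of peak values.

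**Conclusion.** The point holds as an unresolved conflict within the SAP. Section 7.2 states a positive, unqualified selection rule for safety data, and 11.8.4–11.8.6 call for summaries that this rule would distort. All values are probably intended, but the text does not say so.

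The size is conditional. If 7.2 is applied literally and a scheduled value exists in the window, a retest 2–10 days later is discarded in about 85–86% of combinations, and otherwise the scheduled value is lost. This rests on a uniform scheduled day within ±3 days and equal weight for each lag. With no retest frequency in the documents, the effect on any particular table cannot be estimated. A peak at the selected visit, or an unscheduled value alone in its window, is kept. The exposure is greatest for laboratory tables and smaller for ECG.

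**What to change.** Add to SAP 7.2, before unblinding:

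> The one-value-per-window selection applies only to by-visit summaries. Worst postbaseline grade, shift to maximum, potential-DILI, ALT/AST > 5x ULN and marked-abnormality summaries (11.8.4–11.8.6) use all postbaseline values, scheduled and unscheduled, in the safety reporting period.

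Section 11.8.4 defines that period for laboratory data, but 11.8.5 and 11.8.6 state none, so the addition should say which period applies to vital signs and ECG.

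The cost is this short text and a flag in the analysis datasets. No new data are needed and no clinical rule changes. If all values were already intended, the tables stay as planned and the addition only records it.
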